6.3. Missing data

Item 28. Reporting and assumptions/statistical methods to handle missing data (e.g., multiple imputation)

Missing data on primary outcome: The primary analysis will use BIA as measurement method for which we have minimal missing data. ~~To maximize our effort in preventing missing data on the primary outcome (FM), if a child's measurements at baseline or end-of-study are not available from ADP, we will use the data from BIA.~~ The chosen approach for the primary analysis allows already efficient estimation of the intervention effect under the MAR assumption. Hence, there is no need to perform multiple imputation in the primary analysis. We do not expect any missing values in the variables we need for adjustment in the primary analysis.

6.4. Additional analyses

Item 29. Details of any additional statistical analyses required, e.g, complier-average causal effect analysis

Initial data analyses

The analyses described in this section will be performed prior to starting the primary analysis and on a version of the analysis data set including no information on the intervention group. Therefore, they are allowed to inform the primary analysis.

- 1) The volume measurements of the ADP method are known to be affected by temperature and humidity. The ADP measurement procedure includes a correction for this, but it is unclear whether this correction is sufficiently calibrated. For all ADP assessments, information on temperature and humidity will be available. Hence, it is possible to check the degree of calibration.

This will be based on fitting a regression model with the volume measurement as outcome and temperature, humidity, age, sex and height as covariates. The model is assumed to be of the structure $\alpha + f(\text{temperature, humidity}) + g(\text{age, sex, height})$. The optimal functional form of f and g will be determined by using fractional polynomials. In case of distinct differences of f from 0, the estimate of f will be used to derive a correction formula of the type $V' = V + f(\text{temperature, humidity}) - f(t_0, h_0)$, such that V' can be interpreted as the volume to be expected if the measurement has been performed at temperature t_0 and at humidity h_0 .

- 2) The investigation will be extended to investigate the effect of clothing and fasting time on the volume measurements. There will be no attempt to correct the measured volumes accordingly, as these variables are affected by the choice of the child. A potential impact of clothing will be taken into account in the primary analysis by fixing the measurement method in children who change clothing (i.e. BIA will be used if the child wears different clothing at baseline and end-of-study). No attempts are planned to take the potential influence of fasting time into account.
- 3) The influence of age, sex and height on the primary outcome will be investigated by using the model described for the primary analysis without using the treatment indicator. The optimal function form of height will be investigated by using fractioned polynomials. In case of a distinct difference from a quadratic function, an alternative transformation will be used in the primary analysis. For age and sex, the reduction in the error variance when using these variables will be determined. They will be included in the primary analysis if they imply a reduction of the error variance by more than 5%.

“Drop-out” analysis

In this study there are three different levels of data availability for the outcomes relating to body composition: ADP, BIA and missing. This level plays a role similar to the traditional “drop-out” indicator for longitudinal outcomes in RCTs, and understanding of the association of the levels with child characteristics and time points can contribute to interpreting the robustness of the study results.

The status “missing” with respect to BIA measurements can be further divided into “missing due to drop out from study” and “failure to participate in an assessment”. The distribution of the resulting three-level variable will be described stratified by child characteristics, assessment time points, and intervention group.

Secondary outcomes

The intervention effects on secondary outcomes will be analysed by the same model as used for the primary analysis. The FFM-to-FM ratio will be log-transformed prior to the analysis. For the prevalence

of underweight and overweight/obesity, a logistic mixed model will be used. From these analyses no p-values will be reported.

Analyses of patterns in intervention effect over time (secondary objective no. 2):

The intervention effect at interim will be derived from the model fitted in the primary analysis.

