We selected FM as our primary outcome because the intervention targets four behavioural components (diet, physical activity, screen media use, and sleep) which may all affect FM. In contrast, other aspects of body composition, in particular fat free mass (FFM), is only expected to be affected by the physical activity component. FM was considered a more appropriate primary outcome than weight-based measures (e.g. BMI z-score), because certain intervention components, particularly physical activity, may increase FFM (15), while e.g. the diet intervention may reduce FM. Such beneficial effects on body composition would not be reflected in changes in overall weight-based measures. Therefore, favourable intervention effects could be masked by using weight-based measures as the primary outcome.

We used FM in power calculations instead of FM index (2), because we anticipated that due to the cluster-randomized design, height would be equally distributed across intervention and control groups.

Measurement method for primary outcome:

The primary outcome is assessed by two measurement methods:

- 1) *Air-displacement-plethysmography (ADP) (BODPOD)*. This method has demonstrated a level of agreement with the 4-compartment model comparable to that of dual-energy X-ray absorptiometry in children **with obesity** (16). For logistical and resource reasons, ADP was only applied at baseline and end-of-study
- 2) *Bioimpedance analyser (BIA) (InBody 270)*. BIA is a highly feasible field method for estimating body composition, but it has shown lower agreement than ADP with the gold-standard 4-compartment model **in children with obesity** (16). The BIA method was applied at all three time points.

For the present study, we assume ADP to be the more accurate measurement (16), and the ADP results will therefore be used whenever available. BIA will only be used if no ADP measurement is available, i.e. for children with missing data on ADP at baseline or end-of-study, and for the measurements at the interim time point. Furthermore, as the ADP results are sensitive to the child's clothing, BIA results will be used if a child did not wear the same clothes (e.g. swimwear, light clothing) at baseline and end-of-study.

In the primary analysis of FM, we will use BIA data. ADP measures of FM will be used in pre-specified sensitivity analyses (See item 27e). Further details on reasons for this change are provided in Appendix 1 to this SAP.

Secondary outcomes:

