The distribution of any variable included in any later analysis will be depicted graphically in the overall population and stratified by age and sex. Time varying variables will be also stratified by time point of assessment, and the analysis will be extended to change scores, i.e. differences from baseline to follow-up.

Outliers will be identified visually, and data will be checked for potential explanations. In case of explanations indicating an undue effect of external factors, outliers might be removed. Any decision of this kind will be documented and included in the supplementary material of the paper.

Consistency checks of individual trajectories

For each longitudinal outcome, the individual longitudinal trajectories of each child will be inspected with respect to a uniform development. Suspicious measurements will be checked.

Check of expectations

The outcomes considered in this study are well-established. Population norms are available and associations with child characteristics are well-established. The distribution of these variables and their association with child characteristics in this study at baseline will be depicted and compared with data from the literature, for example national data on prevalence of childhood overweight and obesity (5), to establish the validity of the measurement methods and evaluate the representativeness of the study sample.

Item 27d. Details of alternative methods to be used if distributional assumptions do not hold, e.g., normality, proportional hazards, etc.

In case of skewed distributions or other anomalies, potential data transformations will be discussed, or additional sensitivity analyses will be defined.

Item 27e. Any planned sensitivity analyses for each outcome where applicable

To evaluate the robustness of our results to the method used to measure body composition, two sensitivity analyses will be conducted:

1. An ADP-only analysis: The analysis will be repeated using FM measured by ADP at baseline and end-of-study. This analysis will include only participants with a valid ADP measurement, i.e. those wearing standard clothing in the BODPOD.
2. A bivariate model combining ADP and BIA measurements at all time-points: This model will include up to five measurements of FM per child (ADP and BIA at baseline, BIA at interim, ADP and BIA at end-of-study).

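### The temperature and humidity correction for ADP volume in SAP section 6.4 (Item 29) is printed with its signs reversed; if triggered and coded as printed, it would double the fitted environmental effect in the ADP sensitivity analyses

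*SAP*

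**What the plan says.** Section 6.4 (Item 29, point 1 of the initial data analyses) sets out a calibration check of the ADP device. It rests on "fitting a regression model with the volume measurement as outcome and temperature, humidity, age, sex and height as covariates". The structure is given explicitly: "The model is assumed to be of the structure $\alpha + f(\text{temperature, humidity}) + g(\text{age, sex, height", with the bracket then closed.

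The correction is conditional: "In case of distinct differences of f from 0, the estimate of f will be used to derive a correction formula". The rule printed is a "correction formula of the type $V' = V + f(\text{temperature, humidity}) - f(t_0, h_0", again with the bracket then closed; in plain notation, V' = V + f(temperature, humidity) - f(t0, h0). Its purpose is stated in the same sentence: "such that V' can be interpreted as the volume to be expected if the measurement has been performed at temperature t_0 and at humidity h_0".

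Version 2 of the SAP changed where ADP data are used. Section 6.1 now has BIA for the primary analysis and says "ADP measures of FM will be used in pre-specified sensitivity analyses (See item 27e". Item 27e in section 6.2 lists two such analyses: a bivariate ADP and BIA model, and an ADP-only analysis, of which it says "The analysis will be repeated using FM measured by ADP at baseline and end-of-study". Section 6.1 also provides for ADP sensitivity analyses of FFM, FM index, FFM index, FFM-to-FM ratio and FM percentage. The correction formula is not struck out in version 2, and Item 29 is not among the revised items listed at the front of the SAP or in Appendix 1.

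**The concern.** The formula and the interpretation attached to it cannot both be right. V is the regression outcome and f is an additive part of its mean, so f is already contained in V. To move a measurement to reference conditions, one takes out f at the actual conditions and puts in f at the reference conditions. The printed formula does the opposite.

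At stake is the credibility of the method-robustness evidence. Version 2 moved the primary analysis from ADP to BIA and offers the two ADP-based analyses as its check on that change. The correction comes into play only when miscalibration is judged distinct, which is when a reversed sign does most damage to the ADP values.

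**Working it through.** **Inputs, all from section 6.4, Item 29, point 1**
- Model: V = alpha + f(t, h) + g + e, where t and h are temperature and humidity at the measurement, g depends on age, sex and height, and e is residual error.
- Target: the volume expected for the same child at (t0, h0), which is V_ref = alpha + f(t0, h0) + g + e.
- Printed formula: V' = V + f(t, h) - f(t0, h0).

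**Algebra.** Write d = f(t, h) - f(t0, h0).
1. Uncorrected: V - V_ref = d.
2. Printed formula: V' = alpha + 2f(t, h) - f(t0, h0) + g + e, so V' - V_ref = 2f(t, h) - 2f(t0, h0) = 2d.
3. Signs reversed: V - f(t, h) + f(t0, h0) = alpha + f(t0, h0) + g + e = V_ref, so the deviation is 0.

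The printed formula therefore does not yield the quantity the SAP says it yields, for any f that varies with conditions and whether the effect is positive or negative.

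**Numerical check.** The SAP gives no size for f, so the following are assumptions for illustration only: linear f with coefficients 0.05 per degree and 0.01 per humidity point, then both negative; temperature mean 22 and SD 2; humidity mean 45 and SD 10; (t0, h0) = (22, 45). The sample size of 909 is the number of baseline ADP measurements in Table S1 of Appendix 1.

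| f used in the correction | Coefficient sign | RMSE from V_ref, uncorrected | Printed formula | Ratio | Signs reversed |
|---|---|---|---|---|---|
| Known | positive | 0.140 | 0.281 | 2.00 | 0 |
| Known | negative | 0.140 | 0.281 | 2.00 | 0 |
| Estimated by least squares | positive | 0.140 | 0.250 | 1.78 | 0.077 |
| Estimated by least squares | negative | 0.140 | 0.332 | 2.36 | 0.051 |

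With f estimated, the RMSE ratio scatters around 2 because of estimation error in f. The fitted slopes, however, double exactly. In the positive case, refitting the model to the printed V' moves the temperature slope from 0.0107 to 0.0213 and the humidity slope from 0.0116 to 0.0231. In the negative case they move from -0.0684 to -0.1367 and from -0.0136 to -0.0272. With the signs reversed, all the refitted slopes are zero to rounding.

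**From volume to fat mass.** The SAP does not state its conversion. Assume a two-compartment form, FM = weight x (c1/density - c2), with density = weight/V. Then FM = c1 x V - c2 x weight, which is linear in V. An error of 2d in volume becomes 2 x c1 x d in fat mass, against c1 x d uncorrected. The ratio was again 2.00 at c1 = 4.95 and at c1 = 5.30, with f known. This holds on the kilogram scale. For log-transformed FM (Table 1, footnote 1) and for the FFM-to-FM ratio, the factor is only approximately 2, and only when the error is small.

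**The case against.** The best defence is that the aim is stated correctly in words and the formula is introduced only as being of a certain type. An analyst working from the stated aim would subtract f, and refitting the model to the corrected volumes would expose doubled slopes at once. On this view it is a slip of notation and not a wrong method. That is a fair description of how it probably arose, but it does not rescue the text. The loose introduction leaves the form of f open, not its sign. Nor can f be read as the amount to be added, because it is defined as a term in the mean of V.

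The limits on consequence do stand. The device already applies its own temperature and humidity correction, and Item 29 looks only for what is left over. Appendix 1 reports findings on clothing and height and is silent on temperature and humidity.

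Three stronger readings are tempting and are not supported:
- **That the main result is compromised.** It is not. The primary analysis and the main analyses of the secondary body composition outcomes use BIA.
- **That the ADP data, or the Bland-Altman plots behind the move to BIA, were miscorrected.** The SAP does not say whether the correction was triggered, which sign was coded, or whether the plotted values were corrected.
- **That the between-arm contrast is biased.** Baseline (September to November) and end-of-study (March to June) fall in different seasons, and children measured together plausibly share room conditions. But a shift common to both arms is absorbed by the time-point effect in the model of Item 27a. Bias would need conditions to differ by arm within a round, and the SAP gives no evidence of that.

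**Conclusion.** The formula is wrong as written. Under the SAP's own model it has the signs of both f terms reversed and contradicts the interpretation given in the same sentence. If the correction is triggered and coded as printed, the fitted temperature and humidity effect in ADP volume is multiplied by 2 when it should go to 0. The same factor carries to ADP fat mass in kilograms if the conversion is linear in volume.

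The factor of 2 needs no assumption about the size of f. The absolute error cannot be given, because the SAP reports neither f nor the spread of conditions. The affected results are the ADP-only and bivariate sensitivity analyses, for FM and the other body composition outcomes. The ADP-only analysis admits standard clothing only, which Table S1 puts at 587 baseline and 708 end-of-study measurements (587 + 708 = 1,295). The factor does not depend on these counts. Severity is minor to moderate: a definite error in a live rule, confined to robustness checks and conditional on the correction being used.

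**What to change.** In section 6.4, Item 29, point 1, replace the formula with V' = V - f(temperature, humidity) + f(t0, h0).

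State in the SAP or in the supplement to the paper whether the correction was applied, which sign was coded, and whether the ADP values plotted in Appendix 1 were corrected. A simple safeguard is to refit the calibration model to V' and confirm that the temperature and humidity effects have vanished.

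If the printed sign was used, recompute ADP volume and fat mass, and the measures derived from them, before running the ADP-only and bivariate analyses. If the correction was not applied, or was coded with the right sign, only the text changes. The cost is one line of text and, at most, one line of code and a rerun of the ADP derivations; no new data are needed.

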3.6. Timing of outcome assessments

Item 15. Time points at which the outcomes are measured including visit “windows”

The study includes three measurement rounds:

- Baseline assessment (month 0): September–November 2023.
- Interim assessment (month 6–8, end of school year 1): May–June 2024.
- End-of-study assessment (month 18–20, end of school year 2): March–June 2025.

Description of the measurement procedures at each round can be found in the study protocol (2).

Section 4: Statistical principles

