6.2. Analysis methods

Item 27a. What analysis method will be used and how will the treatment effects be presented

Analysis of *longitudinal the primary outcomes (FM)* will be conducted using a mixed linear regression model. Fixed effects are the time point, the intervention group, the interaction between time point and intervention group, ~~an indicator for the type of measurement used~~, and potential covariates (cf. Item 27b) ~~the covariates mentioned in Item 27b~~. Random effects are school, class, and child specific intercept and slope (with respect to time as a continuous covariate). The covariance matrix of the random intercept and the random slope is allowed to vary freely between the two intervention groups. The error variances are allowed to vary over time and between the intervention groups. ~~The error variance is allowed to vary between ADP and BIA measurements, and a constant difference in variance is assumed~~. The interaction between time point and intervention will be parametrized as time point specific intervention effects. The randomization will be taken into account by restricting the intervention effect at baseline to 0, ~~the difference of the variance of the random intercept between the intervention groups, and the difference in error variances at baseline between the intervention groups to 0~~.

Results of the *primary* analysis will be reported by the effect estimate together with a 95% confidence interval and a p-value of the null hypothesis of no intervention effect based on a Wald test. ~~The treatment effect will be phrased as "difference in mean change between the intervention and control group". In case of using log-transformed outcomes, the treatment effect will be transformed as $(\exp(.)-1)*100$ allowing an interpretation as the "difference in mean percentage change". The boundaries of the confidence interval will be transformed accordingly.~~

The structure of the model:

- Reflects the potential effects of school and classes on the outcome.
- Takes the correlation between measurements from the same child into account.
- ~~Allows using the known association of the primary outcome with height and a potential association with age or sex to increase the power by using them as covariates (if relevant)~~.

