- Allows to include all children from the primary analysis population in the *primary* analysis independent of missing values in the *primary* outcome at some time point (including baseline) – ~~except for those missing the outcome at all time points~~.

- Requires only to assume missing at random (MAR) with respect to missing values in the primary outcome.
- Takes into account the use of two different measurement methods for the primary outcome.

Computations will be based on the default settings of the mixed command in Stata. In case of convergence problems, the complexity of the model will be reduced by the following steps until the convergence is reached: 1) Removal of variance components with estimates on the boundary. 2) Equal error variances across at the two follow up time points. 3) Equal error variances across the intervention groups. 4) Equal correlation between random intercept and random slope across the intervention groups.

The weights (estimated inverse probabilities of participation using register data, described in Item 27b) will be incorporated using the pweight option.

With respect to analyses using both BIA and BODPOD measurements, a corresponding bivariate model will be used (see sensitivity analysis, cf. section 27e). This will require modelling a potential systematic difference between the two measurements.

Item 27b. Any adjustment for covariates

The statistical power of RCTs can be improved by adjusting for (strong) prognostic factors. The approach described above implies already an adjustment for baseline variables. Consequently, there is only a need to adjust for factors which improve the prediction of the outcomes after adjustment for baseline values. Consequently, although FM and some of the secondary outcomes are known to be highly influenced by height, this does not necessarily imply a need to adjust for height.

The decision to adjust for potential prognostic factors will be based on an empirical investigation, whether the prediction of the outcome at the final time point can be improved by adding the factor to a model including the baseline values. Improvements of the adjusted R^2 by at least 0.1 will be regarded as an indicator for inclusion as covariate in the analysis model. The potential prognostic factors considered are height, weight, BMI, age and sex.

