| | Baseline | | Interim | | End-of-study | |
|-----------------------|--------------|------------|--------------|------------|--------------|------------|
| | n | % | N | % | n | % |
| ADP available | 909 | 67 | NA | - | 1,039 | 76 |
| Clothing 1 (standard) | 587 | 43 | NA | - | 708 | 52 |
| Clothing 2 (project) | 204 | 15 | NA | - | 231 | 17 |
| Clothing 3 (other) | 118 | 9 | NA | - | 100 | 7 |
| BIA available | 1,274 | 94 | 1,225 | 90 | 1,197 | 88 |
| Total | 1,359 | 100 | 1,359 | 100 | 1,359 | 100 |

Table S1. Number of measurements of primary outcome across measurement methods, measurement rounds and ADP clothing categories.

Table S1 shows that the total number of ADP measurements is substantially lower than the number of BIA measurements. A notable proportion of children declined the ADP assessment because they found the BODPOD intimidating.

In our efforts to investigate the impact of clothing, Bland–Altman plots stratified by clothing category and height were generated to assess agreement between BIA and ADP. These plots indicated that agreement varied systematically with both clothing category and child height (see Figure S1). These findings highlighted the impact of clothing, leading us to consider only clothing category 1 as valid. Consequently, less than half of participants had valid ADP measurements at baseline (43%) and approximately half at end-of-study (52%) (Table S1).

Bland-Altman plots by height/clothing

[figure not shown]

Figure S1: Bland–Altman plots showing agreement in fat mass between air-displacement plethysmography (ADP; fmbodpod) and bioelectrical impedance analysis (BIA; fmbia), stratified by clothing category (1, 2, 3) and height (120, 130, 140, 150 cm).

Given i) the considerable numbers of children with missing data on ADP under the validity restriction concerning clothing; and ii) the systematic differences between ADP and BIA related to clothing and height, we decided that the primary analysis of the intervention effect on FM will only include BIA measurements.

To be completely transparent and to examine the robustness of the study results on the selection of measurement method for the primary outcome, we will include two pre-specified sensitivity analyses:

- i. An ADP-only analysis: The primary analysis will be repeated using FM measured by ADP at baseline and end-of-study. This analysis will only include the participants with a valid ADP measurement, i.e. those wearing standard clothing in the BODPOD.

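### The 5% error-variance rule for age and sex in SAP Item 29(3) looks at a variance that cannot show their prognostic value, and it conflicts with the adjusted R² rule in revised Item 27b

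*SAP*

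**What the plan says.** Item 29(3) in section 6.4 examines how age, sex and height relate to the primary outcome "by using the model described for the primary analysis without using the treatment indicator". For age and sex the decision rule is: "They will be included in the primary analysis if they imply a reduction of the error variance by more than 5" per cent.

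Item 27a in section 6.2 defines that model. "Random effects are school, class, and child specific intercept and slope (with respect to time as a continuous covariate"). It then treats the residual part separately: "The error variances are allowed to vary over time and between the intervention groups". In this SAP, error variance therefore means the within-child residual, distinct from the covariance of the child intercept and slope.

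Item 27b, revised in version 2.0, gives another rule, applied to prediction of the final outcome once baseline is in the model: "Improvements of the adjusted R^2 by at least 0.1 will be regarded as an indicator for inclusion as covariate in the analysis model". Its candidates include the same two variables: "The potential prognostic factors considered are height, weight, BMI, age and sex". Item 29 is not among the items that the revision table or Appendix 1 lists as changed.

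**The concern.** The SAP gives precision as the reason for adjusting: a covariate is worth including if it improves prediction of the outcome beyond the baseline value. A screen for that purpose should look at the variance of end-of-study log fat mass (FM) given baseline log FM. Item 29(3) looks instead at the within-child residual of a model in which every child already has an intercept and a slope. Sex and baseline age do not vary within a child, so the screen is close to blind to them.

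Two further problems follow from the text. The model has several error variances, so the quantity to be compared with 5% is not defined. And Items 29(3) and 27b can give different answers for the same covariate, with nothing to say which one decides. At stake are a little precision and a clear pre-specification of the primary model.

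**Working it through.** The 5% is a decision threshold, so there is no figure in the plan to reproduce. All variance components below are assumptions, because the SAP gives none.

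**1. Algebra.** For child i at time t, let log FM = μ(t) + x(β0 + β1·t) + b0 + b1·t + e, with x constant within the child. If x is left out:
- intercept variance rises by β0²·Var(x);
- intercept–slope covariance rises by β0·β1·Var(x);
- slope variance rises by β1²·Var(x);
- Var(e) does not change.

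For a constant or linear-in-time effect the expected fall in error variance from adding x is therefore zero, whatever the variance components.

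**2. Where the explained variance goes.** Assume child-intercept SD 0.35, slope SD 0.08 per year, error SD 0.10, and a sex difference of 0.25 at baseline plus 0.04 per year. Var(sex) = 0.25.
- Intercept variance: 0.25² × 0.25 = 0.015625, and 0.015625 / (0.1225 + 0.015625) = 11.3% (simulated: 11.7%).
- Slope variance: 0.04² × 0.25 = 0.0004, and 0.0004 / (0.0064 + 0.0004) = 5.9% (simulated: 5.9%).
- Error variance (simulated): 0.00% with sex, 0.09% with sex by visit.

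**3. One common error variance, other inputs.** Simulated fits used 1,359 children with missingness as in Table S1 ("BIA available | 1,274 | 94 | 1,225 | 90 | 1,197 | 88"), six runs per scenario. Assumptions: intercept SD 0.40, slope SD 0.08, residual SD 0.08 (also 0.04 and 0.02), sex difference 0.2 to 0.4, age effect 0.10 to 0.25 per year, no school or class effects.
- Baseline age plus sex: mean fall in error variance −0.04% to +0.07% (single runs −0.22% to +0.17%), while the intercept variance fell by 8% to 29%.
- Age at measurement plus sex: −0.3% to 0.6% at residual SD 0.08, 2.2% at 0.04 and 8.0% at 0.02. Within a child, age at measurement differs from time point only through visit date within each window (for the last round: "End-of-study assessment (month 18–20, end of school year 2): March–June 2025").
- Exception: with sex entered by time point and a sex difference departing from linearity by 0.05, the mean fall was 4.85% (runs 4.35% to 5.44%).

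**4. Time-specific error variances, as Item 27a has them.** Without treatment, three error variances remain. With the three intercept–slope parameters that makes six parameters for the six distinct elements of a 3×3 child covariance, so the model is only just identified. Results from 400 complete-data runs per scenario with constant effects:

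| Residual SD | At least one error variance falls >5% | Mean of the three falls >5% |
|---|---|---|
| 0.08 | about 50% of runs | 16% |
| 0.15 | about 28% | 3.5% |

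The expected fall here is still zero; these passes are sampling noise. If the sex difference is 0.02 larger at interim only, the interim error variance falls by about 14% and the baseline one rises.

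**5. The quantity that matters.** Use the inputs of step 2 with end-of-study at 1.6 years (assumed, within months 18–20), so the sex difference there is 0.25 + 0.04 × 1.6 = 0.314.
- With sex: Var(Y0) = 0.1325; Cov = 0.1225; Var(Y1) = 0.1225 + 0.0064 × 2.56 + 0.01 = 0.1489. Conditional variance = 0.1489 − 0.1225²/0.1325 = 0.0356.
- Without sex: Var(Y0) = 0.1481; Cov = 0.1225 + 0.25 × 0.25 × 0.314 = 0.1421; Var(Y1) = 0.1489 + 0.25 × 0.314² = 0.1735. Conditional variance = 0.1735 − 0.1421²/0.1481 = 0.0372.
- Reduction: 4.1%. Standard error ratio √(1 − 0.041) = 0.979, about 2% lower. R² gain = 0.0015/0.1735, about 0.009.

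In the step 3 scenarios the adjusted R² gain from age and sex was 0.00 to 0.03.

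**The case against.** The strongest reply is that revised Item 27b already screens age and sex on close to the right quantity, and that the 5% sentence looks like a remnant of version 1.0. It sits beside a default quadratic height adjustment that the revised Item 27b no longer takes for granted, and Appendix 1 says that the role of covariates had been overstated. Much of this stands: the plan as a whole does not ignore prediction given baseline. But Item 29 is not listed as revised, and section 6.4 says that its analyses may inform the primary analysis. If the sentence is a remnant, deleting it is still the remedy.

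A reader might infer that Item 29(3) is certain to exclude age and sex. The SAP does not support that. Its error variances are time-specific and can move by more than 5% through noise or a non-linear sex pattern. It also says age, not baseline age, and age at measurement can lower the residual a little, passing 5% only at an extreme residual SD of 0.02.

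It is also fair to say that little depends on the outcome. On the inputs of step 5, sex would fail a 5% cut on conditional variance (4.1%) and the 0.1 cut of Item 27b (0.009).

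**Conclusion.** The point holds as a minor one. The Item 29(3) criterion cannot detect the prognostic value of sex and baseline age. With one common error variance it would in practice exclude them; with the time-specific error variances of Item 27a the answer is noise-driven and the quantity is undefined. It also conflicts with Item 27b on the same covariates.

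The zero expected change rests on algebra alone, for effects that are constant or linear in time. The sizes rest on assumed variance components: about 4% lower conditional variance and about 2% lower standard error at child level, less once school and class variance are counted. A reader might infer bias or a material loss of power. Neither follows: leaving out sex or age does not bias the randomised comparison, and the likely gain in precision is small.

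**What to change.** Delete the error-variance criterion from Item 29(3) and state one rule for age and sex, in one place. Either:
- pre-specify sex and baseline age, each by time point, as covariates in the primary model; or
- keep a single screen on the allocation-free data set, judged on the unexplained variance of end-of-study log FM given baseline log FM, with one stated threshold that also replaces or matches the rule in Item 27b.

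In either case, say whether age means age at baseline or at measurement. The cost is a few sentences of SAP text. Both variables are already collected for the baseline table, and two covariates at three time points use six coefficients among 1,359 children.
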